5.7 Follow-up

Two months after randomisation, parents will be contacted by the researcher to make arrangements for the first follow-up assessment. Follow-up assessments will take place at a time which is convenient for the parent and their child. A final follow-up interview will be conducted 12 months after randomisation.

Follow-up interviews will be carried out through face-to-face interviews. Any travel costs or other reasonable expenses incurred by the parents will be reimbursed. In addition to these assessments, all study participants will be contacted nine months after randomisation using their preferred method (text, email, letter, phone call), to thank them for their participation, to remind them of the plan for their final follow-up interview and to ask them to let us know of any changes in their contact details.

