5.6 Randomisation

Researchers at each site will enter the results of the baseline assessment on a web-based Case Report Form. Remote web-based randomisation will be undertaken through a fully automated service operated by Uni Research (Norway). The allocation ratio for the study is 2:1:1 such that equal numbers of participants are allocated to enhanced treatment as usual and music therapy and, among those allocated to music therapy, equal numbers will be allocated to high and low-intensity treatment. Randomisation will be made in blocks, with block size randomly assigned to between four and eight. Following randomisation the UK-based trial coordinator will be informed which arm of the trial the participant has been assigned to. Parents and therapists will then be given information about allocation status and arrangements made for delivering parent counselling sessions. For those in one of the two active arms of the trial, arrangements will also be made for delivering music therapy sessions. Study researchers are based in separate departments to those involved in organising treatment, helping to ensure they remain masked to the allocation status of study participants.

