11.5 Rate of recruitment

The aim is to recruit 100 participants over a 12 month period. With the support of Clinical Studies Officers from the Mental Health Research Network, two full-time researchers one covering sites in London, the other covering sites in Cambridge and Essex, will each aim to recruit 50 participants during this period. Previous research among children with autism suggests that meetings need to be arranged with eight parents/ families for every five children that will take part in the trial [11], which means that each researcher will need to meet with an average 1.6 parent/ families each week. Data from recruitment sites indicate that the numbers of children they assess each year who have autism spectrum disorder and are within this age group are well in excess of this (see section 10 above).

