12.2. Outcome measures

The primary outcome measure is the severity of autism symptoms using the social communication algorithm which is derived from the ADOS [1], which will be assessed by a trained researcher who is masked to allocation status. We have selected this measure because of its strong psychometric properties including sensitivity to change [1], and because it has been widely used in other randomised trials of children with autism [11-13]. Secondary outcomes are:

- 1) Social Responsiveness Scale [14] a carer based assessment of the severity of autism spectrum symptoms that has high inter-rater and test-retest reliability [15-16]
- 2) Questionnaire on Resources and Stress Friedrich Short Form a widely used measure of parental stress that has been validated among parents of children with autism [17].

3) Warwick and Edinburgh Well Being Schedule, a short validated measure of mental well-being [33].

All outcome measures will be assessed at baseline, 2, 5 and 12 months.

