19.0 APPROVAL BY ETHICS COMMITTEE

Multi-Centre Research Ethics Committee approval will be obtained prior to the start of data collection. Only children whose parent or guardian agrees to provide written informed consent will be included in the study. The parent of each potential participant will be provided with a copy of a Patient Information Sheet that includes a contact number for the study team. The trial will be conducted in accordance with Good Clinical Practice guidelines.

Risks and benefits for trial participants

Each study participant will have the same chance of being allocated to the three trial arms and all parents will be offered the three parent counseling sessions. By taking part in this trial participants and their families will be helping us find out whether music therapy helps children with Autism Spectrum Disorder. If music therapy is effective, this is likely to change the way that children with ASD are treated in the future. If it is not, then the results of the study will help to ensure that fewer children are given ineffective treatments in the future.

Study participants will be asked to give up their time to take part in study interviews and to complete study questionnaires. Baseline assessment takes no longer than 60 minutes observing children and no longer than 120 minutes with parents. Follow-up assessments will require no more than 90 minutes with children and 120 minutes with parents. All parents/ guardians will be offered a £20 honoraria following completion of the 12-month follow-up interview.

As we will collect information on a range of sensitive personal matters such as mental health and behavior we ensure that data is collected and stored carefully. Baseline data will be entered onto a web-based Case Report Form that will not include the patient's name or other information that could identify them. All data will be stored on a secure dedicated web server (based in Norway). Access will be restricted by user identifiers and passwords (encrypted using a one way encryption method). All electronic databases will use a patient identification number rather than the participant's name. Hard copies of data sheets linking the patient identification number to the person's contact details will be kept securely in a locked filing cabinet in a locked office at each participating site, and will only be accessible to a small number of people who are involved in the study.

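### The only stated masking safeguard does not cover disclosure by parents, to whom the rater of the primary ADOS outcome is probably exposed before the 5-month rating

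*Protocol*

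**What the plan says.** - **Masked observer rating.** Protocol section 12.2 makes the ADOS social communication algorithm the primary outcome, "which will be assessed by a trained researcher who is masked to allocation status". Section 2.0 sets the primary end-point at 5 months. Sections 2.0, 5.1 and 7.0 describe the trial as researcher-blind.
- **Parents know the arm.** Section 5.6: "Parents and therapists will then be given information about allocation status".
- **The safeguard.** Section 5.6: "Study researchers are based in separate departments to those involved in organising treatment, helping to ensure they remain masked to the allocation status".
- **Contact with parents.** Section 5.7: two months after randomisation, "parents will be contacted by the researcher to make arrangements for the first follow-up assessment". On the mode of follow-up: "Follow-up interviews will be carried out through face-to-face interviews". Section 19.0 gives the length: "Follow-up assessments will require no more than 90 minutes with children and 120 minutes with parents". Outcomes are collected at 2, 5 and 12 months (section 12.2).
- **Staffing.** Section 11.5 provides "two full-time researchers one covering sites in London, the other covering sites in Cambridge and Essex", each aiming to recruit 50 of the 100 UK children. Section 21.2 gives the same two people the lead in recruitment, assessment and follow-up.
- **Video.** Section 6.4 provides for recording and independent rating of therapy and counselling sessions, for fidelity. It does not mention the ADOS.

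**The concern.** Separate departments block leakage from the people who organise treatment. They do not block leakage from the family, which is the more likely source: the parent knows the arm, and in the music therapy arms the child may attend up to 20 or 60 sessions (section 6.2). The protocol does not mention asking families to keep the arm to themselves, an order for the ADOS and the parent interview, recording of unmasking, or masked scoring of a recorded ADOS.

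At stake is the only primary outcome. A rater who knows the arm can score differently without intending to, and any net shift goes straight into the estimated treatment effect. These are matters of trial conduct. A later statistical analysis plan cannot examine unmasking that nobody recorded at the visit.

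**Working it through.** The protocol gives no figure for masking, so there is none to reproduce. The check has two parts.

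**1. Tracing the roles**

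| Step | Who | Section |
|---|---|---|
| Told the allocation | Parents, therapists, UK trial coordinator | 5.6 |
| Arranges the first follow-up | The researcher | 5.7 |
| Meets parent, up to 120 minutes per follow-up | Face to face; interviewer not named separately | 5.7, 19.0 |
| Rates the ADOS | A trained, masked researcher | 12.2 |
| Leads recruitment, assessment and follow-up | Two full-time researchers, one per region | 11.5, 21.2 |

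No other ADOS rater appears. With one researcher per region, the person who meets the parent at 2 months is probably the person who rates the child at 5 months. This is an inference from the table. No sentence states it.

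**2. Scale, for illustration only**

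Assumptions that are not in the protocol: no true effect, equal groups, a normal approximation, and a net spurious difference of 0.10 to 0.15 SD in favour of music therapy. Such a difference is the share of treated children with an unmasked rater times the rating shift when unmasked. For example, 25% × 0.4 SD = 0.10 SD, and 50% × 0.3 SD = 0.15 SD.

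Inputs from the protocol: 300 children in the whole trial and 100 in the UK (sections 11.3, 11.4). Allocation is 2:1:1, so the control and combined music therapy groups are equal in size (section 5.6).

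Formulas, with n per group: SE = √(2/n). Error rate = 1 − Φ(1.96 − shift/SE) + Φ(−1.96 − shift/SE).

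- **UK arm alone, 50 v 50.** SE = √(2/50) = 0.20. Shift/SE = 0.50 and 0.75. Error 7.9% and 11.7%.
- **Whole trial, 150 v 150, only the UK third affected.** SE = √(2/150) = 0.115. The shifts dilute by 100/300 to 0.033 and 0.050 SD. Error 6.0% and 7.2%.
- **Whole trial, every site affected.** SE = 0.115, undiluted shifts of 0.10 and 0.15 SD. Error 13.9% and 25.5%.

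**The case against.** The strongest reply is that this is an omission and not an error. Section 5.6 claims only that the arrangement helps to keep researchers masked. Section 7.0 says the UK arm uses the same basic methods as the main trial, whose cited protocol is not at hand and may contain more. That stands in part: one can say only that this document does not mention further safeguards, not that none exist. It does not remove the point, because this document sets out who contacts parents and states one safeguard that misses them.

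Several stronger readings are tempting and are not supported:

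- *The ADOS rater is the parent interviewer.* A reader might take this as stated. It is not. Section 5.6 speaks of researchers at each site, and section 11.5 adds support from Clinical Studies Officers for recruitment. The inference is reasonable but remains an inference.
- *The researcher telephones parents and books every visit.* Section 5.7 names the researcher only for the first follow-up and gives no mode of contact. A phone call appears only as one option for the nine-month reminder.
- *The trial's false-positive rate is 14 to 25%.* The mechanism rests on UK staffing. Those figures hold only if all sites work the same way, and the protocol does not describe assessors elsewhere.
- *Unmasked assessments should be dropped in a sensitivity analysis.* Unmasking happens after randomisation and probably differs by arm, so dropping those children could itself introduce bias.

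**Conclusion.** The point holds as a risk that the protocol leaves open, not as a demonstrated failure of masking. The one safeguard covers treatment organisers, while the rater of an observer-scored primary outcome is probably exposed to parents who know the arm, including at 2 months before the primary rating.

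The size cannot be derived from the protocol. Under the assumed shifts, the inflation is modest for the UK data alone, which are to be reported separately (sections 16.2 and 21.2), and small for the pooled trial if the problem is confined to the UK. It is large only if all sites share the arrangement. If the sponsor already intends different people to rate the ADOS and to meet the parents, most of the concern falls away once the protocol says so. The change is worth making because it is cheap and because unrecorded unmasking cannot be reconstructed reliably afterwards.

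**What to change.** Amend sections 5.6, 5.7 and 12.2 of the protocol:

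1. Where feasible, the trial coordinator, who already knows the allocation, or other staff who do not rate the ADOS, arrange the follow-up visits. Ask parents before every contact not to reveal the allocation.
2. At each follow-up, give and score the ADOS and lock it in the web-based case report form before any parent interview.
3. After scoring, record any unmasking, when it occurred, and the rater's guess of the arm. Step 2 does not undo a disclosure at an earlier visit. Where a rater has already been unmasked, have the other regional researcher rate the 5-month ADOS if feasible.
4. Report unmasking by arm. Treat any analysis by unmasking status as exploratory only, for the reason given above about selection after randomisation.

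The cost is protocol wording, a few extra items on the case report form and a fixed order of tasks at visits. The coordinator takes on modest extra booking work: at most 100 × 3 = 300 UK visits, against a trial manager costed part-time in section 21.2, which is why step 1 says where feasible. No additional post is needed. Swapping raters between regions would involve some travel.

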6.0 STUDY INTERVENTIONS

6.1 Improvisational music therapy

The TIME-A trial will examine the clinical effectiveness of improvisational music therapy. This form of music therapy was originally developed in Britain in the 1950s by Paul Nordoff and Clive Robbins and was subsequently refined by [name] and colleagues [3]. It is a child-centred treatment approach which utilises the potential that making music has to enhance social engagement and the expression of emotions [3]. This approach to music therapy is the one most widely used in the NHS for children with autism. Small-scale trials of the intervention have reported positive effects [4-6].

Music therapy sessions in the trial will last for 30 minutes and involve therapists attuning to the child's behaviour through improvisational techniques including making co-improvised music.

Individual sessions will be delivered to the child in local NHS facilities. During sessions music played or sung by the therapist is generally attuned to the child's musical or other behaviours and includes techniques to engage the child and establish a connection with them. To this end the 'musical' features of the child's expression (such as rhythm, melodic patterns, timbre etc) may be mirrored, reinforced or complimented, thus allowing for moments of synchronisation between the child and the therapist and giving the child's expressions a pragmatic meaning within the context of the session. While engaging in joint musical activities the child is offered opportunities to develop and enhance their communication skills, including affect sharing, imitation, joint attention, and turn-taking, all of which are associated with development in language and social competency [8,9].

6.2 Treatment intensity

The TIME-A trial involves two active treatment groups in which music therapy sessions are delivered at two different levels of intensity; once a week (low intensity) or three times a week (high intensity). Over the five month treatment period, those in the low intensity treatment arm will receive up to 20 sessions of music therapy and those in the high intensity treatment arm will receive up to 60 sessions. Previous trials of improvisational music therapy based on both high and low intensity treatment have reported positive effects [4,5]. Low intensity treatment is less costly to deliver and requires less commitment from children and their parents, but some therapists argue that treatment delivered more frequently has a greater impact on a child's communication skills and functioning.

6.3 Enhanced treatment as usual

All parents of study participants will receive enhanced treatment as usual; in addition to usual care from primary and secondary services, parents will receive three counselling sessions delivered over a five month period (at baseline, two months and five months). These sessions will be delivered by experienced clinicians who receive regular supervision and comprise psychoeducation, information about support organisations and support in coping with current problems. This type of support is recommended for parents of children with ASD [7], and will help ensure that all study participants receive a basic level of support across all study centres.

6.4 Treatment fidelity

To determine whether treatment is delivered as intended, therapists will document significant events, notable child behaviours and interventions used after every session. In addition to these self-reports all music therapy and parent counselling sessions will be video-taped to allow for assessment by independent raters. Notes and video-recordings will be used during monthly supervision sessions and video-recordings will be monitored by the lead music therapist in the study. The video recordings shall only be stored for 1 year after the study's results have been published.

7.0 STUDY DESIGN

TIME-A is a three-arm, parallel group, researcher-blind, randomised controlled trial, that will be nested within a larger international study. Using the same basic methods as the TIME-A study [32], the UK arm of the study will involve recruiting 100 participants and following them up five and 12 months after randomisation.

Within the MRC-framework for the evaluation of complex interventions [34], the TIME-A trial is a 'stage 3' pragmatic randomised trial. The interventions are being delivered in the way that they are currently being delivered within the NHS. Outcome measures have been restricted to key outcomes and the main analysis will use the intention to treat principal.

8.0 TARGET POPULATION

The study population is children aged between 4:0 and 6:11 who have autism spectrum disorder and are in contact with NHS services.

9.0 INCLUSION/EXCLUSION CRITERIA

To maximise generalizability of study findings a broad inclusion criteria has been used and number of exclusion criteria have been limited to essential features which are not compatible with using the intervention or participating in the trial. To take part in the study children need to be:

- Aged 4:0 to 6:11 years.
- Have a clinical diagnosis of autism spectrum disorder made by a child psychologist or clinical psychologist according to ICD-10 criteria and confirmed using the Autism Diagnostic Observation Schedule [1], and two of the three domains of the Autism Diagnostic Interview-Revised [2].

Exclusion Criteria

- Received music therapy in the last year.
- Severe sensory disorder: we will exclude children who have severe visual or hearing impairment as this would prevent them from being able to make full use of the intervention we are testing.
- Those who do not have a parent or guardian who is able and willing to provide written informed consent to take part in the trial.

10.0 STUDY SETTING

Study participants will be recruited from NHS healthcare services. These will mainly be Child Development Centres which provide the main point of access for assessment and diagnosis of children with developmental delay, and out-patient clinics provided by child and adolescent mental health services.

Data from community paediatricians in each study site indicate that they receive 80 to 120 referrals of children with ASD each year of whom half are aged 4:0 to 6:11. Child and Adolescent Mental Health Services receive a further 10 to 20 referrals per year of children who would meet study inclusion criteria. The music therapy service in London that covers two of the study sites (Kensington and Westminster) currently receives over 70 referrals a

year of children with ASD, most of whom meet study inclusion criteria. Across the six study centres this equates to referral of over 390 potential participants during the 12 month recruitment phase of the study.

11.0 SAMPLING

11.1 Selection of study sites

The study sites have been selected for the following four reasons:

- i. Each site works with sufficient numbers of children with autism spectrum disorders to enable us to recruit the required sample within the available time frame using two full-time researchers (one based in London, the other based in Cambridge/ Essex).
- ii. In each area, music therapists are already delivering improvisational music therapy to children with autism spectrum disorders in accordance with the treatment approach being tested in the TIME-A study.
- iii. There is strong organisational support for conducting the study among local clinicians and managers.
- iv. Recruitment sites cover a range of inner city, urban, suburban and more rural communities, including relatively deprived parts of inner London, more affluent London suburbs and mixed areas of east and central England.

11.2 Selection of study participants

Children aged 4:00 to 6:11 years have been selected because previous research suggests that this intervention is effective when delivered to children in this age range [3-6].

11.3 Sample size calculation for the main trial

A total sample of 300 needs to be recruited in the study as a whole. Previous trials of improvisational music therapy for children with ASD have reported medium effect sizes associated with active intervention. A Cochrane review of music therapy for children with ASD calculated a Standardised Mean Difference of 0.50 for gestural communication skills and 0.36 for verbal communication skills [6].

A sample of 235 patients will provide 90% power to detect a medium effect size of the intervention on the social communication scale of the ADOS score at 12 months with a 5% level of statistical significance [32]. To take account of possible clustering at the level of study therapists and study centres and a drop out we have inflated the total sample required to 300. Loss to follow-up in trials of psychosocial intervention for children with autism spectrum disorder tends to be low. The PACT trial of parent mediated communication focused treatment reported a follow-up rate of 96% at 13 months [11].

11.4 Sample size for the UK arm of the study

To achieve a total sample of 300 participants in the main trial, it has been calculated that 100 participants will need to be recruited in the UK. This sample will also be large enough to provide valuable information about the clinical effectiveness of delivering this intervention in the NHS.

11.5 Rate of recruitment

The aim is to recruit 100 participants over a 12 month period. With the support of Clinical Studies Officers from the Mental Health Research Network, two full-time researchers one covering sites in London, the other covering sites in Cambridge and Essex, will each aim to recruit 50 participants during this period. Previous research among children with autism suggests that meetings need to be arranged with eight parents/ families for every five children that will take part in the trial [11], which means that each researcher will need to meet with an average 1.6 parent/ families each week. Data from recruitment sites indicate that the numbers of children they assess each year who have autism spectrum disorder and are within this age group are well in excess of this (see section 10 above).

